#### 11.4.4 Secondary Analyses

The same GLMM models as for the primary outcomes will also be used to compare all patient-level secondary outcomes between the intervention groups. NH-level outcomes will be compared between allocation groups by mean of t-tests if the outcomes follow a normal distribution, by means of Mann-Whitney otherwise.

#### 11.4.5 Interim analyses

No interim analyses are planned.

#### 11.4.6 Safety analysis

At the end of the trial, all the participant-level safety outcomes will be compared between intervention groups by means of the same GLMM models mentioned above. Mortality and hospitalisation rates (NH-level) will be compared using t-tests or Mann-Whitney tests, as appropriate (see section 11.4.4).

Causes of hospitalisation will be described, but no statistical tests will be performed in this outcome.

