## **5.4 Safety Outcomes**

Safety outcomes are:

1. The mortality rate, defined as the number of participant having died between baseline and completion of the follow-up period, divided by the total number of participants;
2. The hospitalisation rate, defined as the number of participant having been hospitalised between baseline and completion of the follow-up period, divided by the total number of participants;
3. The number of days spent in hospital between baseline and completion of the follow-up period;
4. The causes of hospitalisation;
5. The number of falls between baseline and follow-up;
6. The proportion of participants having experienced at least one fall;
7. The number of falls in participants having fallen at least once;
8. The number of days where restraints measures have been used.

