### **8.5 Data Collection and Follow-up for withdrawn participants**

No further data collection will occur for participants withdrawing from the study. Data already collected will be anonymised and used in the analysis.

Withdrawn participants will be monitored as usual by the NH care team.

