#### **9.2.4.2 Hospitalisation rate**

All hospitalisations will be documented by the NH nurse using the follow-up CRF, by reporting the beginning and end dates for each hospital stay. If no hospital stay occur during the trial period, the follow-up CRF will be completed accordingly. Elective hospitalisations will be excluded from analysis. The number of participants having been hospitalised will then be computed, and the hospitalisation rate calculated.

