#### **9.2.4.5 Number of falls**

The number of falls having occurred to each participant will be reported in the CRF for follow-up data collection. The number of falls for each group will then be computed by the investigators.

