#### 11.4.3 Primary Analysis

The comparison of the primary outcome (change in number of PIMs between baseline and 4 months) between groups will be performed by means of generalised linear mixed models (GLMM), with patient representing a random effect clustered within NH and the allocation group as a fixed effect.

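### Falls and restraint days are compared as raw counts with no time at risk, so counts cut short by death or hospital stay are read as full 16-week counts

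*Combined protocol and SAP*

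**What the plan says.** Section 5.4 lists three safety outcomes as totals without a denominator: "The number of falls between baseline and follow-up", "The number of days spent in hospital between baseline and completion of the follow-up period" and "The number of days where restraints measures have been used". Section 9.2.4.5 adds a group total: "The number of falls for each group will then be computed by the investigators".

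Section 11.4.6 states that "all the participant-level safety outcomes will be compared between intervention groups by means of the same GLMM models" already described. Section 11.4.3 describes that model "with patient representing a random effect clustered within NH and the allocation group as a fixed effect". Section 11 names no distribution, link, offset or exposure variable.

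Planned follow-up is 16 weeks from visit 1 in both arms (9.3.2). Under 9.2.5, when a resident dies the follow-up CRF is completed within 7 days, and the same procedure applies to a resident who is in hospital on the visit date. For withdrawal, section 8.5 says "No further data collection will occur for participants withdrawing from the study", and data already in hand are used. Hospital stays are documented "by reporting the beginning and end dates for each hospital stay" (9.2.4.2). The only missing-data rule (11.5) is multiple imputation of outcomes missing at random in more than 5% and less than 40% of participants.

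**The concern.** A count over a fixed window is a fair measure only if everyone is observed for the whole window. Here a death in week 4 leaves a 4-week count, and the plan gives it the same standing as a 16-week count. Multiple imputation does not help, because the value is observed, only short. Hospital days act in a similar way. The NH record is the source for falls and restraints (12.1.2), and the restraints defined in 9.2.4.8 include detectors placed in the resident's room, so a resident in hospital is in practice not at risk of either outcome as recorded.

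When lost time differs between arms, the arm with less time at risk shows fewer events for that reason alone. This matters because the synopsis lists the number of falls among the main secondary outcomes. There is also no data safety monitoring committee (1.6) and no interim analysis (11.4.5), so the end-of-trial comparison is the only planned comparison of safety between the arms.

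**Working it through.** **Sample size, from the plan.** Section 11.2 expects half of 18 NHs, a mean of 59 beds and 20% recruitment: 9 × 59 × 0.20 = 106.2, which reproduces the stated 106. With 1:1 allocation (6.2.1) that is 53 per arm. The plan gives no power calculation, fall rate, death rate or dropout rate to reproduce.

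**Expected ratio.** Suppose the true event rates are equal and a share d of an arm leaves early, at times spread uniformly over follow-up. Mean time at risk is then 1 − d/2 of the 16 weeks, and the expected raw-count ratio (intervention/control) is

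(1 − d_int/2) / (1 − d_ctl/2).

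All shares below are assumptions.

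| Early exits, control vs intervention | Calculation | Raw-count ratio |
|---|---|---|
| 5% vs 5% | 0.975/0.975 | 1.00 |
| 5% vs 10% | 0.950/0.975 | 0.974 |
| 5% vs 15% | 0.925/0.975 | 0.949 |
| 10% vs 20% | 0.900/0.950 | 0.947 |
| 5% vs 30% | 0.850/0.975 | 0.872 |

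Swapping the arms inverts the ratio: 15% in control against 5% in intervention gives 0.975/0.925 = 1.054. Exits at a constant hazard, with mean exposure d/(−ln(1 − d)), give nearly the same values: 0.974 for 5% vs 10%, 0.944 for 10% vs 20% and 0.863 for 5% vs 30%.

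**Does an offset remove it?** Simulations used 1,500 trials per scenario, 53 per arm, overdispersed counts with an assumed mean of 0.8 falls per full follow-up, and a true rate ratio of 1.

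- Deaths 5% vs 15%: ratio 0.951 without exposure, 1.003 with it.
- Exits 10% vs 20% (negative binomial, dispersion 1, no NH effect): 0.95 without the offset, 1.00 with it. The false-positive rate is 5.1% and 5.0%.
- Exits 5% vs 30% (same model): 0.88 without, 1.01 with.

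**Size against noise.** With mean 0.8 and dispersion 1, the variance of a count is 0.8 + 0.8² = 1.44. The standard error of the log ratio is √(2 × 1.44/53)/0.8 = 0.29. A 95% interval therefore spans a factor of about exp(1.96 × 0.29) ≈ 1.8 either way. The bias at 5% vs 15% is ln(0.949) = −0.052, or 0.052/0.29 ≈ 0.18 standard errors.

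**The case against.** The strongest reply is that the effect is small and needs an imbalance that nothing in the documents predicts. Both parts are right. A threefold difference in deaths moves the ratio by about 5%, well inside the sampling error. This limits the importance of the point. It does not justify leaving out an offset.

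The plan is also silent rather than explicit. It calls allocation a fixed effect, not the only one, and a generalised linear mixed model can carry an offset. That is a fair reading, and a reason to write the offset down before the analysis.

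Four stronger readings are tempting, and the documents do not support them.

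- *Withdrawn residents' shortened counts enter the analysis.* Falls, hospital stays and restraint days go on the follow-up CRF (9.2.4.2, 9.2.4.5, 9.2.4.8), and 9.3.2 places the part on death, falls and hospitalisation at visit 2. Section 9.2.5 orders early completion only for death or hospitalisation at the visit date. A resident who chooses to stop is offered only the quality-of-life and complaints questionnaires. The counts are therefore more likely missing, and subject to 11.5, than shortened. A partial count is not impossible, because the withdrawal itself is noted on that CRF (9.2.3.11).
- *The protocol expects more deaths under the intervention.* The evidence it cites in 3.4 and 3.7 points to lower mortality. In that case raw counts would make the intervention look worse on falls, not better.
- *Hospital days are biased in the same direction.* Death ends the accrual of hospital days, but terminal stays add to it. The net direction is unknown.
- *The arm with more deaths would look safer overall.* Mortality is compared separately (11.4.6), and withdrawals are counted (5.3).

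**Conclusion.** The omission is real and minor. Falls and restraint days have no denominator, the model has no stated exposure term, and deaths demonstrably shorten the counts. The resulting bias favours the arm with less time at risk and can run either way. It is about 3% to 5% for a 5 to 10 point imbalance in early exits, about 13% for 25 points, and nil when losses are equal.

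These figures rest on assumed exit shares, on exit times that are uniform or at constant hazard, and on event rates unrelated to the risk of leaving. They apply directly to deaths. They extend to withdrawals only where a partial count is in fact recorded. No direction is claimed for hospital days. This is a cheap improvement to a safety analysis, not a threat to the trial's conclusions.

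**What to change.** In 11.4.6, specify the following.

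- **Falls:** a count mixed model (negative binomial or Poisson, log link, NH random effect) with log(days at risk) as offset. Days at risk run from baseline to the earliest of death, withdrawal or visit 2, minus days in hospital. Subtract every stay, including the elective ones that 9.2.4.2 excludes from the hospitalisation outcome.
- **Restraint days:** analyse relative to the same days at risk, by offset or as a proportion of days. The proportion respects the fact that restraint days cannot exceed days at risk.
- **Hospital days:** report per day of follow-up alive, next to mortality, so that the two are read together.
- **Withdrawals:** apply the same exposure rule where a partial count exists; otherwise treat the count as missing under 11.5.
- **Reporting:** rate ratios with 95% confidence intervals, and total days at risk by arm beside the group total of falls in 9.2.4.5.

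The cost is SAP wording and one derived variable. Hospital dates are already collected. The protocol text records that deaths and withdrawals occurred but does not say that their dates are captured. If the follow-up CRF lacks them, add two date fields or take the dates from the NH record, which is already the source document for deaths (12.1.2).

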| Investigators:                         | [name]
Centre de Pharmacie Communautaire,
Policlinique Médicale Universitaire,
[name]
[contact]
[contact] (secretary)

[name]
Centre de Pharmacie Communautaire,
Policlinique Médicale Universitaire,
[name]
[contact]
[contact]                            |
| Study Centre:                          | This study is monocentric; however, the intervention will take place in different NHs of the Cantons of Vaud and Fribourg.   |
| Statistical Considerations:            | Generalised linear mixed models will be used for the analysis of outcomes relative to individual participants; outcomes at the NH level will be analysed using t-tests or Mann-Whitney, according to distribution.   |
| GCP Statement:                         | This study will be conducted in compliance with the protocol, the current version of the Declaration of Helsinki, the ICH-GCP as well as all national legal and regulatory requirements.   |

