## 6. STUDY DESIGN

### 6.1 General study design and justification of design

This study is a randomised, controlled trial of a deprescribing intervention, consisting of a pharmacist-led, deprescribing-focused medication review, resulting in the creation, validation and application of a personalized deprescribing plan by the NH care team. The study will take place in NHs already included in the intervention arm of the OLD-NH-QC-DeMo study (see section 3.1, page 13), as it aims to test the cumulative effect of the medication review and the deprescribing quality circle tested at the NH level in the QC-DeMo study. All stakeholders in the NH will have to agree for the NH to take part in the IDel study; agreement will be documented in writing (

The participants will be residents of the participating NHs which are prescribed the most drugs (see chapter 7, page 19 for details), and thus most at risk of PIM use [41-44]; if NH care team judges that discussing the possibility of deprescribing with a specific resident will destabilise her/him, this resident will be excluded from participation. The residents will be offered the option to participate in descending order of number of drugs prescribed (from most drugs prescribed to least), based on a ranking prepared by the NH pharmacist. After inclusion, participants will be randomly allocated to either the control or intervention groups, based on pre-specified, NH-specific randomisation lists (see section 6.2.1 below for details). Inclusion will continue until 20% of the residents of the NH have been included. An estimated 100 residents will be included in the study, based on a mean of 50 residents per NH and 10 NH participating in the study.

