### 6.2 Methods of minimising bias

#### 6.2.1 Randomisation

Participants will be randomised between the intervention and control groups at the time of inclusion, in a 1:1 ratio at the level of the NH. For each NH agreeing to participate, a randomisation list of length equal to 20% of the number of beds of the NH will be generated by the investigators, using the tool provided at [www.randomization.com](http://www.randomization.com). These lists will be created using randomly permuted blocks, to ensure a relative equilibrium between groups, even in case of incomplete inclusion in the NH. The lists will then be loaded in the REDCap randomisation module for this institution.

Allocation will be made at the end of completion of the inclusion CRF by the NH nurse (see Annex 10).

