### **7.3 Assignment to study groups**

After recruitment, participants will be randomised between control and intervention groups. Randomisation will be made using the inclusion CRF; after randomisation, the allocation group will be recorded in a NH-specific list, to be stored with the study documents. This list will comprise the name of the

participants, their identifying code and allocated group. Allocation will be communicated to the treating physician and the participants.

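### Mortality and hospitalisation are labelled nursing-home-level and tested by t-test or Mann-Whitney, although residents are randomised individually within each home and both outcomes are defined per participant

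*Combined protocol and SAP*

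**What the plan says.** On the test, section 11.4.6 reads "Mortality and hospitalisation rates (NH-level) will be compared using t-tests or Mann-Whitney tests, as appropriate". It sets these two outcomes apart from the other participant-level safety outcomes, which go to the generalised linear mixed model (GLMM). The general rule is in section 11.4.4: "NH-level outcomes will be compared between allocation groups by mean of t-tests if the outcomes follow a normal distribution", with Mann-Whitney otherwise. The synopsis repeats it: "outcomes at the NH level will be analysed using t-tests or Mann-Whitney, according to distribution".

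On the design, section 6.1 says "participants will be randomly allocated to either the control or intervention groups, based on pre-specified, NH-specific randomisation lists". Section 6.2.1 provides for each home "a randomisation list of length equal to 20% of the number of beds of the NH", and section 7.3 says "After recruitment, participants will be randomised between control and intervention groups". The 1:1 ratio that section 6.2.1 places at NH level describes balance inside a home; it does not make the home the unit of allocation.

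On the outcomes, section 5.4 defines mortality as "the number of participant having died between baseline and completion of the follow-up period, divided by the total number of participants" and hospitalisation as "the number of participant having been hospitalised between baseline and completion of the follow-up period, divided by the total number of participants". Sections 9.2.4.1, 9.2.4.2 and 12.1.2 have both recorded for each participant, and section 9.2.4.2 leaves elective stays out.

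**The concern.** An NH-level comparison between allocation groups makes sense when homes are allocated to arms. Here they are not. No section defines a rate per home and arm, and none says how the two rates from one home should be treated. The analyst would have to settle the unit and the pairing, possibly after seeing the data.

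The synopsis puts mortality and hospitalisation among the main secondary outcomes, and section 4.5 makes them safety objectives. There is no data safety monitoring committee (section 1.6) and no interim analysis (section 11.4.5), so this final comparison is the planned between-arm test of harm on both. A test that ignores the stratification, or reduces about 106 residents to 18 coarse rates, is less able to show a difference in either direction.

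**Working it through.** **1. The plan's own figure.** Section 11.2 expects half of 18 homes, a mean of 59 beds and 20% recruitment: 18 / 2 = 9 homes, and 9 × 59 × 0.20 = 106.2, which reproduces the stated 106.

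**2. What an NH-level test would work on.**
- One rate per arm: two numbers, nothing to test.
- One rate per home: each mixes both arms, so the arms cannot be compared.
- One rate per home and arm: 9 per arm, each from 59 × 0.20 / 2 = 5.9 residents (106 / 10 / 2 = 5.3 with the synopsis's 10 homes).

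Only the third can be carried out. With 6 residents, a rate takes one of seven values (0/6 to 6/6). With no variation between homes, the chance that it is exactly zero is 0.9^6 = 53% at a 10% risk and 0.8^6 = 26% at a 20% risk.

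**3. Assumptions for the size of the loss.** The documents give neither event risks nor between-home variation, so these are assumed: overall risks as shown; a home effect shared by both arms with SD 0, 0.3, 0.5 or 1.0 on the logit scale; 9 homes; arm size per home drawn from {4, 5, 6, 6, 7, 8}, equal within a home; two-sided 5%; 20,000 replicates. A replicate in which a test is undefined counts as no rejection.

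**4. Tests.** The t-tests use the home-by-arm rates. The participant-level test is Mantel-Haenszel (MH) stratified by NH. With x₁ events among n₁ intervention residents, n₀ controls, t events in all and N = n₁ + n₀ in a home, the statistic is (Σx₁ − Σn₁t/N)² / Σ[n₁n₀t(N − t) / (N²(N − 1))], referred to chi-square on 1 df without continuity correction.

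**5. Results (%), at SD 0 / 0.3 / 0.5 / 1.0.**

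| Quantity | Unpaired t | Paired t | Stratified MH |
|---|---|---|---|
| Power, 10% vs 20% | 27 / 25 / 22 / 14 | 24 / 24 / 24 / 23 | 30 / 30 / 31 / 34 |
| Power, 10.5% vs 30% | 66 / 64 / 60 / 45 | 61 / 61 / 61 / 61 | 73 / 73 / 74 / 78 |
| Type I error, 15% risk | 4.8 / 4.1 / 3.3 / 1.4 | 5.0 / 4.6 / 4.6 / 4.3 | 4.7 / 4.6 / 4.7 / 4.9 |
| Type I error, 5% risk | 4.1 / 3.6 / 3.1 / 1.8 | 4.0 / 3.6 / 3.3 / 2.5 | 4.6 / 4.5 / 4.5 / 4.3 |
| 95% CI half-width, 15% vs 15% (points) | 14.6 / 15.0 / 15.6 / 17.9 | 15.6 / 15.6 / 15.4 / 14.6 | 13.3 / 13.2 / 13.1 / 12.4 |

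Subtracting the rounded powers gives the loss against MH, to within about a point:
- 10% vs 20%, unpaired: 30 − 27 = 3, 30 − 25 = 5, 31 − 22 = 9, 34 − 14 = 20 points.
- 10% vs 20%, paired: 6, 6, 7 and 11 points.
- 10.5% vs 30%, unpaired: 7, 9, 14 and 33 points.
- 10.5% vs 30%, paired: 12, 12, 13 and 17 points.

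Mann-Whitney, the likelier choice for such coarse rates, does a little worse than the unpaired t-test: 25 / 20 / 13% for 10% vs 20% at SD 0 / 0.5 / 1.0.

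**6. Sensitivity.** With 10 homes (arm sizes {3, 4, 5, 6, 6, 8}), power for the moderate difference stays within 1 point of the table and for the large one within about 2. With continuity correction, MH power falls to 21 / 21 / 22 / 23% (moderate) and 64 / 64 / 64 / 69% (large).

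**The case against.** The strongest reply is that the loss depends on how the text is read and on the comparator chosen.

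- *Individual data.* Section 5.4 defines one rate over all participants, so the t-test might be meant for individual 0/1 values. Power would then be 31 / 30 / 31 / 30% for 10% versus 20%, close to MH, with type I error of 3.5–5.1%. The arithmetic is right, but this reading contradicts the NH-level label and still ignores the home.
- *Comparator.* Continuity-corrected MH has no more power than the paired t-test at any SD for the moderate difference, and less than the unpaired test at SD 0 and 0.3. This stands, so the gain claimed here is for the uncorrected test, which kept its level in every null scenario examined.
- *Unit.* Section 11.4.4 speaks of comparing allocation groups, which points to home-by-arm rates, and Mann-Whitney suggests an unpaired test. Both are fair inferences, but neither is written down.
- *Simpler fix.* The GLMM already in the plan could be used with a binomial family. This is defensible, but the likelihood-ratio test of a logistic mixed model rejects too often when events are few: 8.9 / 8.4 / 6.9% at a 5% risk for SD 0 / 0.5 / 1.0. The cause is that test with sparse events, not the home effect: a plain logistic likelihood-ratio test with 53 per arm has an exact type I error of 8.6%. A Wald test errs the other way, at about 0.2%.
- *Size.* The losses of 20 and 33 points need SD 1.0 and the unpaired reading. At SD 0.5 or less, the moderate-effect loss is 3–9 points on roughly 30% power. That is correct.

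**Conclusion.** The concern holds. The NH-level label contradicts the randomisation scheme and the outcome definitions, and no other section repairs it. This mismatch rests on the text alone and needs no assumption.

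Its size does rest on assumptions. Under those used here, either home-level t-test has less power than an uncorrected participant-level test stratified by NH: by about 3 to 20 points (unpaired) or 6 to 11 points (paired) for 10% versus 20%, and by 7 to 33 or 12 to 17 points for 10.5% versus 30%. The unpaired test becomes conservative as homes differ more, down to a type I error of 1.4% at a 15% risk and SD 1.0. No false-positive inflation is involved and the primary analysis is untouched. The trial's low power for these outcomes is a separate matter that a better test does not cure. This should be fixed before the data are analysed.

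**What to change.** In sections 11.4.4 and 11.4.6 and the synopsis, remove the NH-level t-test and Mann-Whitney rule for these two outcomes. State instead that death and non-elective hospitalisation are participant-level binary outcomes with one pre-specified analysis:

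- **Estimate:** Mantel-Haenszel risk difference stratified by NH, with a 95% CI using the Sato variance. With weight w = n₁n₀/N in each home, it is Σw(x₁/n₁ − x₀/n₀) / Σw. Coverage in the simulations was 93.1–95.6%, except for 10.5% versus 30%, where it was 94.5 / 94.2 / 93.7 / 91.7%.
- **Test:** Mantel-Haenszel stratified by NH, without continuity correction.
- **Sensitivity analysis:** stratified exact mid-p test. It is cautious when events are few (type I error 2.3–2.8% at a 5% risk) and has power of 29 / 27 / 30 / 32% for 10% versus 20%.
- **No events:** report counts only.
- **Supportive only:** logistic mixed model with a random intercept for NH, because of its error rate with few events.

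Two additions would keep the text consistent. Say how participants who withdraw are handled for these outcomes, since section 8.5 stops their data collection and section 11.5 would bring in multiple imputation. Consider the same method for the proportion with at least one fall, which is also binary.

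The cost is a few sentences in three places and a little more analysis. No new data are needed, because deaths and hospital stays are already recorded per participant.

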## STUDY SYNOPSIS

|                                      |  |
|--------------------------------------|--|
| Sponsor-Investigator          | Dre [name]
Pharmacist
Centre de Pharmacie Communautaire,
Policlinique Médicale Universitaire,
[name]   |
| Study Title:                  | Randomised, Controlled Trial of an Individual Deprescribing Intervention for Nursing Homes' Residents.   |
| Short Title/Study ID:         | OLD-NH-IDel study  |
| Protocol Version and Date:    | Protocol version 2 of 27.08.2018   |
| Trial registration:           | The study will be registered with ClinicalTrials.org; no registration number available at the time of submission. In addition, this study will be registered with the Swiss National Clinical Trial Portal (KOFAM).  |
| Study category and Rationale  | As the study involves minimum risk for the participant and will be conducted under the constant supervision of health professionals, this study is deemed of risk category A.  |
| Clinical Phase:               | Not applicable to this study   |
| Background and Rationale:     | Older people residing in nursing homes (NH) are frequently polymedicated and often prescribed potentially inappropriate medications (PIMs). Deprescribing has been proposed as a way to reduce the number of drugs they receive and their exposure to harmful treatments.

In the nursing homes of Vaud and Fribourg, physicians, nurses and pharmacists are already working together in quality circles to improve drugs use. This provides an excellent opportunity to implement a deprescribing intervention, using the collaboration already in place. |
| Objectives:                   | The primary study objective is to determine the effect of a pharmacist-led, deprescribing-focused medication review on the use of PIMs by NH residents.

The main secondary objectives are to determine the safety of this intervention and its effect on the participants' quality of life.   |
| Outcomes:                     | The primary outcome is the change in the number of PIMs used by participants between baseline and 4 months (end of follow-up).

The main secondary outcomes are the mortality rate, hospitalisation rate, number of falls and quality of life measured with EQ-5D-5L. This intervention will also be evaluated on implementation outcomes.   |

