### **3.4 Clinical Evidence to Date**

Deprescribing has already been shown to be an effective way to reduce the number of drugs used by older people living in NH: an Australian study randomised 95 participants to a deprescribing intervention or usual care [32]. Participants in the intervention group received a lower number of drugs ( $-2.0 \pm 0.9$ ) 12 months after intervention than participants in the control group. This reduction did not increase mortality, falls or hospital admissions, and did not negatively influence cognitive functions, quality of life or sleep.

A 2016 systematic review found that deprescribing could be safely enacted in older people [15]: in randomised trials, individual deprescribing interventions led to a lower mortality, without lowering cognitive functions, increasing the risk of falls, or increasing the occurrence of adverse events.

Studies indeed show that enacting deprescribing induces very little acute adverse events: in a study of deprescribing in 422 NH residents in the United Kingdom [33], only seven adverse events occurred following the discontinuation of more than 700 medicines. None of those seven events led to significant harm to the residents; the measures taken to resolve these events included the reinstatement of the stopped medication, the treatment of a urinary tract infection, the adaptation of an insulin regimen, and closer monitoring of blood pressure. In the previously cited trial of deprescribing in Australian NHs [32], there were no differences in the occurrence of adverse events between the intervention and control groups.

These findings were confirmed by a recent study of deprescribing in Dutch NHs residents [23]: reducing the number of medication prescribed to 159 NH residents did not worsen their clinical condition or their quality of life, compared to 193 residents which were not subject to the deprescribing intervention.

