#### **4.5 Safety objectives**

This study aims to assess the safety of the deprescribing intervention in terms of mortality, hospitalisation, falls and the use of restraints.

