### 11.2 Determination of Sample Size

No data on the repartition of the number of PIMs used by NH residents in Vaud and Fribourg are available prior to the study. This, no power calculation can or determination of the sample size needed can be made in advance.

We anticipate that half of the 18 eligible NH will agree to take part in the study; with a mean number of beds of 59 in these NHs, the recruitment of 20% of the population should lead to the inclusion of 106 residents.

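### Mortality and hospitalisation, the core of the safety objective, are answered only by difference tests on about 53 residents per arm, with no interval, margin or bound to show what harm is excluded

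*Combined protocol and SAP*

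**What the plan says.** The synopsis ranks safety among the leading aims after the primary one: "The main secondary objectives are to determine the safety of this intervention and its effect on the participants' quality of life". Section 4.5 lists what is meant: "This study aims to assess the safety of the deprescribing intervention in terms of mortality, hospitalisation, falls and the use of restraints".

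The statistical answer is in section 11.4.6 and has two parts. For most outcomes, "all the participant-level safety outcomes will be compared between intervention groups by means of the same GLMM models mentioned above". For the two most serious outcomes, "Mortality and hospitalisation rates (NH-level) will be compared using t-tests or Mann-Whitney tests, as appropriate". Causes of hospitalisation are described without testing.

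Section 5.4 defines the mortality and hospitalisation rates as counts of affected residents "divided by the total number of participants", so each is a simple proportion per arm.

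On size, section 11.2 states that no power calculation was possible and that "the recruitment of 20% of the population should lead to the inclusion of 106 residents". Section 11 gives no significance level, confidence interval, non-inferiority margin, upper bound or rule for concluding on safety. Section 1.6 sets up no data safety monitoring committee, and section 11.4.5 plans no interim look.

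**The concern.** A t-test or Mann-Whitney test, with nothing further specified, answers one question: was a difference detected? The safety objective needs a different answer: how large an excess of deaths or hospitalisations is still compatible with the data? In a trial of this size the two come apart. A non-significant result is likely when there is no harm, and also likely when the harm is substantial.

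The final comparison is the only between-arm safety evidence the trial will produce. If the report gives only p-values, a statement of no significant difference in mortality would leave readers unable to tell reassurance from lack of information. The trial concerns the withdrawal of medicines from frail residents, so that distinction matters to anyone who uses the result.

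The point does not depend on which test or unit of analysis is chosen. It concerns what can be concluded from the result.

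**Working it through.** **Inputs from the documents**

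- Sample size (11.2): half of 18 homes, 59 beds, 20% recruited. 9 × 59 × 0.20 = 106.2, which reproduces the stated 106. Section 6.1 uses 10 homes of 50 residents: 10 × 50 × 0.20 = 100.
- Allocation (6.2.1): 1:1 within each home, so about 53 per arm (50 on the 6.1 figures).
- Follow-up (9.3.2): 4 months.

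**Assumptions, because the documents give no figure**

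- Alpha: two-sided 0.05.
- Control 4-month mortality: 3% to 20%. The only anchor is section 3.4, where mean stay is under 3 years. With a constant exit rate and a 36-month mean, 4-month exits are 1 − exp(−4/36) = 10.5%. A mean of 30 months gives 12.5% and one of 24 months gives 15.4%. These are exits for any cause among all residents, so about 10% mortality is plausible but not established.
- Harm to be detected: a doubling, used as an illustration.

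**Step 1: chance of missing a doubling**

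Normal approximation at 10% v 20%, n = 53 per arm, pooled proportion 0.15:

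- SE under no difference = √(2 × 0.15 × 0.85 / 53) = 0.0694
- SE under the doubling = √((0.10 × 0.90 + 0.20 × 0.80) / 53) = 0.0687
- z = (0.10 − 1.96 × 0.0694) / 0.0687 = −0.52, so power is 30% and the miss rate 70%

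Exact enumeration of the chi-square test over all pairs of binomial counts, counting only significant results in the direction of harm as detection:

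| Control v intervention | Missed, 53 per arm |
|---|---|
| 3% v 6% | 91% |
| 5% v 10% | 85% |
| 10% v 20% | 70% |
| 15% v 30% | 53% |
| 20% v 40% | 37% |

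Counting significance in either direction changes only the first row, to 90%. Fisher's exact test misses more (79% at 10% v 20%).

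The planned home-level tests give much the same answer. Simulating 9 homes with 6 residents per arm each and no between-home variance, at 10% v 20%, the unpaired t-test misses 72% and Mann-Whitney 74%. With 10 homes and 5 per arm, the figures are 74% and 76%.

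**Step 2: what the data could exclude**

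This step needs no assumption about power.

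- Equal deaths, 6/53 v 6/53. The Wilson limits for each arm are 5.3% and 22.6% around 11.3%. The Newcombe interval for the difference is ±√(6.0² + 11.3²) = ±12.8 percentage points. The score interval for the risk ratio reaches about 2.8. A doubling would add 11.3 points, so it is not excluded although p = 1.
- Twice as many deaths, 12/53 v 6/53: Fisher p = 0.20, which would be reported as non-significant.
- 5/53 v 5/53: ±12.1 points. The simple half-width at 10.5% is 1.96 × √(2 × 0.105 × 0.895 / 53) = 11.7 points. Expected precision near 10% mortality is therefore about ±12 points.

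**Step 3: scale of the gap**

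At an assumed 10% control mortality:

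- Excluding a 10-point increase (one-sided 2.5%, 80% power): (1.96 + 0.84)² × 2 × 0.10 × 0.90 / 0.10², about 142 per arm.
- Detecting 10% v 20% with 80% power: about 199 per arm.

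The plan expects about 53.

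**The case against.** Five points on the other side have force.

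- **No decision rule for safety is stated.** A reader might infer that the plan intends to call the intervention safe if the tests are non-significant. The documents do not say so. Section 11.4.6 says only that outcomes are compared, and section 10.2.5 says safety will be assessed in the final report. The supportable claim is that the misreading is left open.
- **Section 3.4 does not show how these investigators will read their own data.** It says of an earlier 95-participant trial: "This reduction did not increase mortality, falls or hospital admissions, and did not negatively influence cognitive functions, quality of life or sleep". It is tempting to treat this as evidence of intent. It is a background summary of another group's study, whose intervals we cannot see, and it is not part of the analysis plan.
- **A GLMM yields an estimate and a standard error.** For falls, hospital days and restraint days an interval follows directly from the planned model, and the defect is only that reporting it is not promised. The objection bites hardest on mortality and hospitalisation.
- **Safety information is not limited to these tests.** Serious adverse events are reviewed individually with a causality assessment (10.1.1, 10.2.1), and causes of hospitalisation are described. This is useful, but it is case-level judgement and gives no between-arm estimate.
- **The lack of power is not concealed.** Section 11.2 and the synopsis both say that no power calculation was done. That is fair, but it makes a statement of precision more useful.

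A reader might also extend the point to quality of life. EQ-5D-5L is listed in 5.2 as a secondary outcome, not among the safety outcomes in 5.4, and the calculations here do not carry over to it.

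**Conclusion.** The concern holds in a bounded form. Safety is a stated main secondary objective, and the plan gives no confidence interval, margin or bound with which to meet it. For mortality and hospitalisation the only inferential tool is a difference test.

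A single unconditional figure, such as a doubling of mortality being missed 70% of the time, would overstate what is known. That figure needs a control mortality of about 10% and a two-sided alpha of 0.05, neither of which is in the documents. Over 3% to 20% the miss rate runs from 91% to 37%. A doubling is missed more often than not at the tabulated rates up to 15%, but not at 20%. The interval result is firmer: with six deaths in each arm, the trial could not exclude an excess of almost 13 percentage points.

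This is worth correcting before the analysis. It does not affect the primary analysis of PIM counts.

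**What to change.** In section 11.4.6:

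- Make the between-arm estimate with a two-sided 95% CI the basis of the safety conclusion. For death and hospitalisation, use the risk difference and risk ratio on participants, as 5.4 defines the rates, in place of the t-test or Mann-Whitney test. For falls, hospital days and restraint days, report the GLMM estimate with its CI.
- Require the report to say which sizes of harm the harm-side limit does and does not exclude.
- Add a sentence such as: a non-significant difference will not be taken as evidence that the intervention is safe.

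In section 11.2, state the expected precision: a 95% CI of about ±12 percentage points for mortality near 10%, with that rate labelled as an assumption.

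Rewording the objective in 4.5 and the synopsis, from assessing safety to estimating the effect on the safety outcomes, is optional.

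The cost is a few sentences, with no extra participants, data or procedures. The downside is that the trial will report a wide interval instead of a simple statement of safety.
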